### 7.2.1 Stopping Rules

The study will be put on temporary hold (defined as a pause in enrolment of the participants) pending further safety data analysis if any SAE or other safety finding is assessed as related to the study intervention that, in the opinion of AstraZeneca, warrants suspension of further dosing of participants until the safety finding is fully assessed.

### 7.3 Lost to Follow up

A participant will be considered lost to follow-up if he or she repeatedly fails to return for scheduled visits and is unable to be contacted by the study site.

The following actions must be taken if a participant fails to return to the clinic for a required study visit:

- The site must attempt to contact the participant and reschedule the missed visit as soon as possible and counsel the participant on the importance of maintaining the assigned visit schedule and ascertain whether or not the participant wishes to and/or should continue in the study.
- Before a participant is deemed lost to follow up, the Investigator or designee must make every effort to regain contact with the participant (where possible, 3 telephone calls and, if necessary, a certified letter to the participant's last known mailing address or local equivalent methods). These contact attempts should be documented in the participant's medical record.
- Should the participant continue to be unreachable, he/she will be considered to have withdrawn from the study.
- Site personnel, or an independent third party, will attempt to collect the vital status of the participant within legal and ethical boundaries for all participants randomized, including those who did not get investigational product. Public sources may be searched for vital status information. If vital status is determined as deceased, this will be documented, and the participant will not be considered lost to follow-up. Sponsor personnel will not be involved in any attempts to collect vital status information.

Discontinuation of specific sites or of the study as a whole are handled as part of [Appendix A](#).

## 8 STUDY ASSESSMENTS AND PROCEDURES

Study procedures and their timing are summarized in the SoA. Protocol waivers or exemptions

are not allowed.

Immediate safety concerns should be discussed with the Sponsor immediately upon occurrence or awareness to determine if the participant should continue or discontinue study intervention.

Adherence to the study design requirements, including those specified in the SoA, is essential and required for study conduct.

All screening evaluations must be completed and reviewed to confirm that potential participants meet all eligibility criteria. The Investigator will maintain a screening log to record details of all participants screened and to confirm eligibility or record reasons for screening failure, as applicable.

Procedures conducted as part of the participant's routine clinical management (eg, blood count) and obtained before signing of the ICF may be utilized for screening or baseline purposes provided the procedures met the protocol-specified criteria and were performed within the time frame defined in the SoA.

Repeat or unscheduled samples may be taken for safety reasons or for technical issues with the samples and must be captured in the EDC system. This may include results from external laboratories where participants have tested positive for COVID-19.

## **8.1 Efficacy Assessments**

### **8.1.1 SARS-CoV-2 Neutralizing Antibody Assessments**

Serum samples to measure SARS-CoV-2 nAb levels will be collected from participants according to visits specified in the SoA ([Table 1](#)). Authorized laboratory will measure nAbs to the SARS-CoV-2 emerging dominant variant(s) circulating during the course of the study, using validated live virus neutralization assays.

### **8.1.2 Participant-reported COVID-19 Symptoms**

To determine the incidence of infection, study sites will contact all participants weekly (telephone/email/text) to check for any COVID-19 symptoms experienced since the last contact and with reminders to monitor and report any COVID-19 symptoms.

During these contacts, the Investigator will assess whether the participants meet the clinical criteria for SARS-CoV-2 infection (adapted from the WHO COVID-19 case definition as defined by WHO 2022 in Clinical management of COVID-19: living guideline) from the past week.

The following criteria adapted from the WHO COVID-19 case definition clinical criteria (WHO 2022):

- Any two of the following: fever (subjective definition to be used for fever), cough, positive COVID-19 test (rapid antigen test or RT-PCR)

OR

- Acute onset of ANY THREE OR MORE of the following signs or symptoms: fever (subjective definition to be used for fever), cough, general weakness/fatigue, headache,

myalgia, sore throat, coryza, dyspnea, nausea/diarrhea/anorexia, conjunctivitis, positive COVID-19 test, symptom as judged by the Investigator to be related to COVID-19.

If, following study intervention administration, a subject develops COVID-19, according to the Provisional recommendations on the methods for prevention, diagnosis and treatment of novel coronavirus infection (COVID-19), issued by the Ministry of Health of the Russian Federation, version 17 dated December 14, 2022 (Provisional recommendations 2022) (s)he must call “122” to be visited by a healthcare professional who, among other procedures, will perform a COVID-19 antigen test or RT-PCR. Once a visit by a healthcare professional has been requested, the subject must notify the study doctor of the date symptoms occurred and the date a healthcare professional visit has been requested, as soon as possible. Also, once a test result is available, the participant must report within 3 days the date of test and its result to the Investigator. If the test result is positive, the Investigator (or his/her delegate, according to the local regulations and institution guidelines) will make telephone calls *every three days* to collect safety data until the subject informs about his/her recovery. **Safety Assessments**

Planned time points for all safety assessments are provided in the SoA (Section 1.3).

### **8.2.1 Physical Examinations**

Full and targeted physical examinations will be performed at the visits as specified in the SoAs (Section 1.3).

- A full physical examination will include, but is not limited to, assessment of height, weight, general appearance, head, ears, eyes, nose, throat, neck, skin, as well as cardiovascular, respiratory, abdominal, and nervous systems. Each clinically significant abnormal finding at screening will be recorded in the medical history in the eCRF.
- A targeted physical examination will include, but is not limited to, areas suggested by the medical history. When there are no new complaints or findings, this should be documented. Each clinically significant abnormal finding from the time of study intervention administration should be reported as an AE per Section 8.3.

### **8.2.2 Vital Signs**

Vital signs, including pulse rate, respiratory rate, blood pressure (on a non-dominant arm after a 10-minute rest in a sitting position), and body temperature will be assessed at the visits as specified in the SoAs (Section 1.3). On the visit 1 day 1, vital signs will be assessed pre-dose and again approximately 10 to 15 minutes after the second injection is given.

Situations in which vital sign results should be reported as AEs are described in Section 8.3.7.

### **8.2.3 Electrocardiogram**

12-lead electrocardiogram will be performed at timelines as specified in the SoA (Section 1.3).

A 12-lead ECG will be obtained after 5 minutes' supine rest, using the site's own ECG machines.

The Investigator will judge the overall interpretation as normal, borderline, or abnormal. If abnormal, it will be documented as to whether or not the abnormality is clinically significant by the Investigator. For all abnormalities (regardless of clinical significance), the specific type and nature of the abnormality will be documented. Clinically significant findings should also be documented on the AE page of the eCRF.

The Investigator may add extra 12-lead resting ECG safety assessments if there are any abnormal findings or if the Investigator considers it is required for any other safety reason. These assessments should be entered as unscheduled assessments.

## 8.2.4 Clinical Safety Laboratory Assessments

The serum chemistry, haematology, and coagulation analyses will be performed at a local laboratory at or near to the study site (see Section 1.3.1). Blood should be taken in the morning on an empty stomach, after 8-14 hours of overnight fast.

Sample tubes and sample sizes may vary depending on laboratory method used and routine practice at the site.

Additional safety samples may be collected if clinically indicated at the discretion of the Investigator. The date, time of collection, and results (values, units, and reference ranges) will be recorded on the appropriate eCRF.

The laboratory variables that will be measured are listed in Table 7.

**Table 7** **Laboratory Safety Variables**

Hematology	
White blood cell (WBC) count	Neutrophils absolute count
Red blood cell (RBC) count	Lymphocytes absolute count
Hemoglobin (Hb)	Monocytes absolute count
Hematocrit (HCT)	Eosinophils absolute count
Mean corpuscular volume (MCV)	Basophils absolute count
Mean corpuscular hemoglobin (MCH)	Platelets
Mean corpuscular hemoglobin concentration (MCHC)	
Serum Chemistry	
Sodium	Alkaline phosphatase (ALP)
Potassium	Alanine aminotransferase (ALT)
Urea	Aspartate aminotransferase (AST)

Creatinine (and estimated glomerular filtration rate [eGFR])	Gamma glutamyl transpeptidase (GGT)
Albumin	Total bilirubin (TBL)
Calcium	Conjugated bilirubin
Phosphate	Tropoenin, high-sensitivity test (screening only)
Glucose (random)	
Coagulation	
Activated partial thromboplastin time (aPTT)	Prothrombin time (PT) (or international normalized ratio)
Other	
HIV test (all subjects)	
Other (women of childbearing potential only)	
Urine or serum ( $\beta$ -hCG) pregnancy test	Follicle stimulating hormone a

a For female participants aged < 50 years who are considered postmenopausal, will be performed at screening if they have been amenorrhoeic for 12 months or more following cessation of exogenous hormonal treatment.

In case a participant shows an AST or ALT  $\geq 3 \times$  ULN together with total bilirubin  $\geq 2 \times$  ULN please refer to [Appendix D](#) for further instructions.

$\beta$ -hCG = beta human chorionic gonadotropin; ULN = upper limit of normal

For WOCBP only, a urine or serum  $\beta$ -hCG pregnancy test will be performed locally at Visit 1. The test must be negative before dosing. A serum pregnancy test may be performed if a urine pregnancy test is not possible.

## 8.2.5 Other Safety Assessments

### 8.2.5.1 Immediate Adverse Events

Participants will be kept under observation for 1 hour after study intervention administration to ensure their safety. Any AE that occurs during this period will be noted on the source document and in the eCRF.

As with any biologic product, hypersensitivity reactions (including anaphylaxis) and injection site reactions are possible. Therefore, appropriate drugs and medical equipment to treat these reactions must be immediately available, and study personnel must be trained to recognize and treat anaphylaxis. Management of anaphylaxis and hypersensitivity should be performed in accordance with current standard of care and clinical guidelines.

Any AEs should be reported as described in Section 8.3.

### 8.2.5.2 Injection Site Reactions

Injection site reactions may be observed and may manifest as local inflammation, redness, itching, pain, swelling, bruising, and possible bleeding or infection at the site of injection. Diameters of any redness/swelling will be recorded.

Injection site reactions will be monitored as specified in the SoAs (Section 1.3). On study day where study intervention is administered, the injection site monitoring will be performed immediately after, 30 minutes (+ 10 minutes), and 1 hour after both injections are complete and also prior to participant release. Injection site reactions will also be monitored on Visit 2 (Day 8).

Any AEs should be reported as described in Section 8.3.

### **8.3 Adverse Events and Serious Adverse Events**

The Principal Investigator is responsible for ensuring that all staff involved in the study are familiar with the content of this section.

The definitions of an AE or SAE can be found in [Appendix B](#).

Adverse events will be reported by the participant (or, when appropriate, by a caregiver, surrogate, or the participant's legally authorized representative or equivalent representative as locally defined).

The Investigator and any designees are responsible for detecting, documenting, and recording events that meet the definition of an AE.

#### **8.3.1 Time Period and Frequency for Collecting AE and SAE Information**

AEs, MAAE, AESI will be collected from the time of study intervention administration throughout the study, up to and including the last visit.

SAEs will be recorded from the time of signing of the ICF throughout the study, up to and including the last visit.

Any AESIs will be specified in the eCRF by Investigator and will be assessed from the time of study intervention (see Section 8.3.4).

If the Investigator becomes aware of an AE/SAE with a suspected causal relationship to the study intervention that occurs after the data collection period specified in the protocol, or after the end of the clinical study in a participant treated by him or her, the Investigator shall, without undue delay, but not later than 24 hours, report the serious adverse event to the Sponsor.

#### **8.3.2 Follow-up of AEs and SAEs**

Any AEs that are unresolved at the participant's last AE assessment in the study are followed up by the Investigator for as long as medically indicated, but without further recording in the eCRF. AstraZeneca retains the right to request additional information for any participant with ongoing AE(s)/SAE(s) at the end of the study, if judged necessary.

#### **Adverse event variables**

The following variables will be collected for each AE:

- AE (verbatim)

- The date and time when the AE started and stopped
- Severity grade/maximum severity grade/changes in severity grade
- Whether the AE is serious or not
- Investigator causality rating against the Investigational Product(s) (yes or no)
- Action taken with regard to Investigational Product(s)
- If the AE caused participant's withdrawal from study (yes or no)
- Outcome

In addition, the following variables will be collected for SAEs:

- Date AE met criteria for SAE
- Date Investigator became aware of SAE
- AE is serious due to
- Date of hospitalization
- Date of discharge
- Probable cause of death
- Date of death
- Autopsy performed
- Causality assessment in relation to study procedure(s)
- Causality assessment to other medication
- Description

Severity ratings will be used, adapted from the CTCAE v5.0 (NIH 2017), and are described in [Appendix B](#).

### 8.3.3 Causality Collection

The Investigator should assess causal relationship between IMP and each AE, and answer 'yes' or 'no' to the question 'Do you consider that there is a reasonable possibility that the event may have been caused by the investigational product?'

For SAEs, causal relationship should also be assessed for other medication and study procedures. Note that for SAEs that could be associated with any study procedure the causal relationship is implied as 'yes'.

A guide to the interpretation of the causality question is found in [Appendix B](#).

### 8.3.4 Adverse Events of Special Interest

Adverse events of special interest will be AESIs will be specified in the eCRF by Investigator and will be assessed from the time of study intervention.

An AESI is an event of scientific and medical interest, specific to the further understanding of the safety profile of the study intervention and requires close monitoring and rapid communication by the Investigators to AstraZeneca. An AESI can be serious or non-serious.

The AESIs for AZD3152 are:

- CCI
- I [REDACTED]

### **8.3.5 Medically Attended Adverse Events**

Medically attended adverse events will be collected according to the time points specified in the SoAs (Section 1.3).

Medically attended adverse events are defined as AEs leading to medically-attended visits that were not routine visits for physical examination or vaccination, such as an emergency room visit, or an otherwise unscheduled visit to or from medical personnel (medical doctor) for any reason. Adverse events, including abnormal vital signs, identified on a routine study visit will not be considered MAAEs.

### **8.3.6 Adverse Events Based on Signs and Symptoms**

All AEs spontaneously reported by the participant or care provider or reported in response to the open question from the study site staff: 'Have you had any health problems since the previous visit/you were last asked?' or revealed by observation will be collected and recorded in the eCRF. When collecting AEs, the recording of diagnoses is preferred (when possible) to recording a list of signs and symptoms. However, if a diagnosis is known and there are other signs or symptoms that are not generally part of the diagnosis, the diagnosis and each sign or symptom will be recorded separately.

Diagnoses of suspected or confirmed COVID-19, confirmed asymptomatic SARS-CoV-2 infection, and/or recurrence of COVID-19 (or of SARS-CoV-2 reinfection) will be collected and recorded in the eCRF as an AE.

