## Number of Participants:

In total, approximately 87 participants will be exposed to a single dose of AZD3152 (300 mg, 2 mL) IM, and 29 participants will be exposed to a single dose of placebo (2 mL) IM.

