### 3 OBJECTIVES AND ENDPOINTS

**Table 4 Objectives and Endpoints**

Objectives	Estimand Descriptions/Endpoints
Primary  To evaluate the safety of AZD3152 compared with placebo	Population: Safety analysis set Endpoints: 

• Occurrence of AEs collected throughout the study

• Occurrence of SAEs, MAAEs, and AESIs collected throughout the study

 Intercurrent events: Treatment policy will be applied, i.e., all events collected will be included in the analysis regardless of the presence and timing of intercurrent events. Summary measure: The number and proportion of subjects with AEs, SAEs, MAAEs, AESIs.
Secondary  To compare the nAb responses to the SARS-CoV-2 emerging dominant variant(s) of concern circulating during the course of the study in serum following AZD3152 or placebo administration	Population: SARS-CoV-2 nAb analysis set Endpoint: Titer for SARS-CoV-2 emerging dominant variant(s) nAbs Intercurrent events: Participants who experience a protocol deviation that can interfere with an antibody response or violate adherence to the assigned dose, become infected, receive COVID-19 treatment or vaccination that can alter nAb levels will have data collected after the intercurrent event set to missing for analysis of this endpoint (i.e., while-on-treatment strategy is applied). Summary measure: Geometric mean titer (GMT) and geometric mean fold rise (GMFRs) (from baseline value through Day 29 after the single IM dose) of SARS-CoV-2 nAbs. Descriptive statistics for the log-transformed titer will include the number of participants, GMT and GMFR, corresponding gSD, 95% CI, minimum, and maximum and summarized by treatment arm.
To compare the incidence of symptomatic COVID-19 cases in participants receiving study intervention. (efficacy)	Population: Full analysis set Endpoint: Incidence of a post-treatment symptomatic COVID-19 case (negative RT-PCR at baseline to positive RT-PCR or positive antigen test at any time up

Objectives	Estimand Descriptions/Endpoints
	CC1  

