# 9 STATISTICAL CONSIDERATIONS

## 9.1 Statistical Hypotheses

The primary objective of the study is to evaluate the safety of AZD3152 compared with placebo. No formal statistical hypothesis was proposed, and the data presentation and analysis will be descriptive in its nature.

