### B 2 Definition of Serious Adverse Events

A SAE is an AE occurring during any study phase (ie, run-in, treatment, washout, follow-up), that fulfils one or more of the following criteria:

- Results in death
- Is immediately life-threatening
- Requires in-participant hospitalization or prolongation of existing hospitalization
- Results in persistent or significant disability or incapacity.
- Is a congenital anomaly or birth defect
- Is an important medical event that may jeopardise the participant or may require medical treatment to prevent one of the outcomes listed above.

Adverse Events for **malignant tumours** reported during a study should generally be assessed as **SAEs**. If no other seriousness criteria apply, the 'Important Medical Event' criterion should be used. In certain situations, however, medical judgement on an individual event basis should be applied to clarify that the malignant tumour event should be assessed and reported as a **non-serious AE**. For example, if the tumour is included as medical history and progression occurs during the study, but the progression does not change treatment and/or prognosis of the malignant tumour, the AE may not fulfil the attributes for being assessed as serious, although reporting of the progression of the malignant tumour as an AE is valid and should occur. Also, some types of malignant tumours, which do not spread remotely after a routine treatment that does not require hospitalization, may be assessed as non-serious; examples in adults include Stage 1 basal cell carcinoma and Stage 1A1 cervical cancer removed via cone biopsy.

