4.2.3.2 Derivations

The following criteria adapted from the WHO COVID-19 case definition clinical criteria (WHO 2022) will be used to determine a symptomatic COVID-19 case:

- Any two of the following: fever (subjective definition to be used for fever), cough, positive COVID-19 test (rapid antigen test or RT-PCR)

OR

- Acute onset of ANY THREE OR MORE of the following signs or symptoms: fever (subjective definition to be used for fever), cough, general weakness/fatigue, headache, myalgia, sore throat, coryza, dyspnea, nausea/diarrhea/anorexia, conjunctivitis, positive COVID-19 test, symptom as judged by the Investigator to be related to COVID-19.

To properly link the onset of symptoms with the laboratory results, a window will be applied to the symptom onset date. For participants who meet the symptomatic criteria listed above, a positive of RT-PCR test or positive antigen test collected within 10 days of COVID-19 symptoms is required to consider the participant meeting the symptomatic COVID-19 case criteria.

Participants who become unblinded to treatment assignment and/or take other non-investigational product(s) for COVID-19 prevention, in both cases prior to having met the criteria for the COVID-19 endpoint, will have data collected after the intercurrent event set to missing for analysis of this endpoint (i.e., while-on-treatment strategy is applied).

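### The any-AE total compared with placebo includes COVID-19 diagnoses, as do the MAAE and SAE totals for some cases, and the SAP names no participant-level count without them (minor)

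*Protocol*

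**What the plan says.** The primary objective is safety against placebo. Protocol Table 4 gives the summary measure as "The number and proportion of subjects with AEs, SAEs, MAAEs, AESIs". Protocol 9.4.2.1 and the endpoint table in SAP 4.2 apply treatment policy, so no collected event is removed, and the arms are compared descriptively. Protocol 9.1 adds: "No formal statistical hypothesis was proposed, and the data presentation and analysis will be descriptive in its nature".

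Three rules bring COVID-19 into these totals:

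- **AE.** Protocol 8.3.6 requires "Diagnoses of suspected or confirmed COVID-19, confirmed asymptomatic SARS-CoV-2 infection, and/or recurrence of COVID-19" to be recorded as an AE.
- **MAAE.** Under Protocol 8.1.2 a participant who develops COVID-19 must call "to be visited by a healthcare professional who, among other procedures, will perform a COVID-19 antigen test or RT-PCR". Protocol 8.3.5 counts an AE as medically attended if it leads to "an otherwise unscheduled visit to or from medical personnel (medical doctor) for any reason".
- **SAE.** Protocol Appendix B 2 includes "Requires in-participant hospitalization or prolongation of existing hospitalization" among the seriousness criteria.

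Symptomatic COVID-19 is also a secondary efficacy endpoint. For it, SAP 4.2.3.2 says "a positive of RT-PCR test or positive antigen test collected within 10 days of COVID-19 symptoms is required".

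SAP 4.2.1.3 lists an overall AE summary; AEs, MAAEs and SAEs by system organ class and preferred term; possibly related versions of these; a table of COVID-19-related AEs; and participant listings. It names no count of participants with any AE, MAAE or SAE other than COVID-19. Protocol 9.4.3 names none either, though it leaves room for further tables in the SAP.

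**The concern.** The cases that AZD3152 is meant to prevent are counted twice: as efficacy events and inside the primary safety totals. If the product works, fewer AZD3152 participants have a COVID-19 AE. The any-AE total then moves in its favour for a reason unrelated to tolerability, and a modest excess of other events could be offset. The any-MAAE and any-SAE totals can move the same way, through the cases seen by a doctor or admitted.

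Preferred-term rows and the COVID-19 table show how many participants had COVID-19. They do not show how many had nothing else, and that number is needed to read the total as a statement about other events.

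**Working it through.** **Plan's own figures.** Protocol 9.2 goes from 108 evaluable to 116 randomised with 5% drop-out: 108 / 0.95 = 113.7, so 114, and the next multiple of 4 is 116. At 3:1 that is 87 and 29, which agrees with the synopsis ("approximately 87 participants will be exposed to a single dose of AZD3152"). The plan gives no figure for the effect examined here.

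**Inputs.** The documents give none of the following, so all are assumed:

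- I, confirmed symptomatic incidence on placebo over six months: 2%, 5%, 10%
- b, rate of other events, equal in both arms: 10%, 35%, 50% for AEs and for MAAEs; 3% for SAEs
- m, share of cases seen by a doctor: 0.5 and 1
- h, share hospitalised: 0.05 to 0.20

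The relative reduction R is 0.7673 (Protocol 2.2.2) or 0.83 (Protocol 2.3.2). Both belong to the predecessor antibody and serve as illustration only. COVID-19 and other events are taken as independent. Suspected but test-negative illness is left out, because it would not be expected to differ by arm.

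**Any AE.** An arm's rate is 1 - (1 - b)(1 - c), where c is I on placebo and I(1 - R) on AZD3152. The difference is (1 - b) × I × R. For b = 10% and I = 10%: 0.90 × 0.10 × 0.7673 = 6.9 points, and with 0.83, 7.5 points.

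| Shift towards AZD3152, points | I = 2% | I = 5% | I = 10% |
|---|---|---|---|
| b = 10% | 1.4–1.5 | 3.5–3.7 | 6.9–7.5 |
| b = 35% | 1.0–1.1 | 2.5–2.7 | 5.0–5.4 |
| b = 50% | 0.8 | 1.9–2.1 | 3.8–4.2 |

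The excess of other events on AZD3152 that would leave the totals equal is about the same size: 7.1 to 7.6 points at b = 10%, I = 10%.

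**Any MAAE.** The shift is (1 - b) × I × m × R. It equals the table at m = 1 and half of it at m = 0.5, so about 0.4 to 7.5 points. A smaller doctor share lowers it further, to zero at m = 0.

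**Any SAE.** The shift is 0.97 × I × h × R: 0.4 to 1.6 points at I = 10% and 0.1 to 0.3 at I = 2%.

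**Sampling error.** The 95% half-width is 1.96 × √[p(1 - p)(1/87 + 1/29)]: 12.6 points at p = 10% and 20.0 at p = 35%. One placebo participant is 1/29 = 3.4 points. Expected placebo cases are 29 × I = 0.58, 1.45 and 2.9. The chance of no placebo case, when no shift towards AZD3152 could appear, is (1 - I)^29 = 56%, 23% and 5%.

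**Why subtraction fails.** One participant can have both kinds of event. Take invented counts of 15/87 and 5/29 with any AE, and two COVID-19 participants per arm. The counts with another AE lie in 13–15 and 3–5. The difference lies between 13/87 - 5/29 = -2.3 and 15/87 - 3/29 = +6.9 points.

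**The case against.** The strongest reply is that nothing here is wrong and most of the information is already planned. Counting COVID-19 as an AE under treatment policy is coherent. An excess of, say, injection-site reactions would appear in its own preferred-term row, which COVID-19 cases do not alter. With few cases expected, the listings show who had only COVID-19. The shift is smaller than sampling error throughout. The upper figures combine high incidence, a low background rate and another antibody's efficacy. Vaccines and prophylactic antivirals are allowed in both arms after the Day 29 assessments, which could narrow the difference.

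All of that stands, and it keeps the point minor. What remains is that the headline total is the primary measure, any shift has a predictable direction if the product works, and a count rebuilt later from listings would have no pre-specified rule for which events are COVID-19. The possibly related tables do not fill the gap: they drop every event judged unrelated, which is a narrower question.

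A reader might infer three stronger things that the documents do not support:

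- **That every COVID-19 case is an MAAE.** Protocol 8.1.2 speaks of a healthcare professional and 8.3.5 specifies a doctor. How often the visitor is a doctor is not stated.
- **That the sponsor has decided against a non-COVID count.** The rows of the overall AE summary are not specified, so one can say only that the SAP names no such count.
- **That the primary estimand is wrong.** The totals do what treatment policy says they do.

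**Conclusion.** The point holds as a minor gap in presentation. COVID-19 diagnoses are in the any-AE total by rule. They are in the any-MAAE and any-SAE totals only for cases attended by a doctor or hospitalised. The SAP names no participant-level count without them, and the named tables cannot supply it by subtraction.

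Under the assumed rates the any-AE shift is about 0.8 to 7.5 points in favour of AZD3152, and the any-SAE shift is at most about 1.6. The direction assumes that AZD3152 prevents COVID-19. The size assumes an incidence, a background rate and independence that the documents do not give, plus a risk reduction borrowed from the predecessor. No test, sample size or decision rule is affected. The consequence is confined to how the descriptive primary contrast is read.

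**What to change.** In SAP 4.2.1.3, beside the unchanged totals, add supplementary rows by arm for participants with any AE, any MAAE and any SAE other than test-confirmed COVID-19 or SARS-CoV-2 infection.

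- Write a COVID-19 term list; the documents contain none. Have blinded staff fix it before the final unblinding, or label the rows post hoc if that has passed. Use the same list to define the table of COVID-19-related AEs.
- Leave an event out of the supplementary rows only if it is on the list and confirmed by RT-PCR or antigen test, so that suspected but unconfirmed illness stays in the count.
- Keep all COVID-19 events displayed, because Protocol 2.3.1 lists antibody-dependent enhancement of infection as a potential risk.
- Footnote that complications coded to other terms remain in the supplementary count and that confirmed asymptomatic infections are excluded from it.
- No AESI row is proposed, because the AESI list is redacted.

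The cost is three rows and one term list, from data already collected. Estimand, endpoints and existing tables do not change. The drawback is that the new count is not a pure measure of tolerability, because COVID-19 complications under other terms stay in it.
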